4.6.2 Analysis Visit Windowing

Post-baseline visits are to be held at Weeks 1, 2, 4, 6, 8 and 10, namely at study Day 7, 14, 28, 42, 56 and 70, within two days from target day. In addition, unscheduled visits and visits of Early Termination may be given. Comprehensive non-overlapping visit windows are defined for Week 4 from Day 14 to Day 42 and for Week 8 as Day 43 or later, respectively, excluding any follow-up visits.

Primary and secondary efficacy endpoints will be summarized and analysed by *analysis visits*. For Week 4 and Week 8, analysis visits are defined as the visits held closest to the target day per analysis visit window as defined above. Any other visits within the same visit window will not be considered for analysis of primary or secondary efficacy endpoints. If the time distances of two visits from the target day are identical, the later visit is selected for analysis.

Other efficacy endpoints and safety endpoints will be summarized and analysed by nominal visits as appropriate.

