2.1 Study Design

This is a prospective, investigational, investigator-blind, vehicle and active-controlled, parallel-group, 3arm, randomized, phase-III trial conducted at approximately 34 sites in the European Union. The trial population consists of subjects fulfilling all inclusion and no exclusion criteria as defined in the CTP, Sections 5.2 and 5.3 with any exceptions documented [1]. Random allocation to one of three parallel treatment groups in a 3:1:3 ratio (MC2-01 cream; MC2-01 vehicle; active comparator) is stratified by site.

A total of 476 subjects are planned to be enrolled, randomized and observed until final evaluation and completion. Subjects prematurely terminating the trial will not be replaced.

The maximum trial duration for each subject will be approximately 14 weeks and includes a screening period of up to 30 days (if washout of prohibited medications is required), an 8-week treatment period, and a follow-up period of 2 weeks.

A total of seven visits and a telephone interview of subjects are planned. The telephone interview is planned for Week 2 (Visit 3), while the visits will be held at screening (Visit 0, Day -30 to 0), randomization (Visit 1, Week 0, Day 0), Visits 2, 4, and 5 at Weeks 1, 4 and 6, respectively, planned for Days 7, 28, and 42 plus/minus 2 days, respectively, Visit 6 as end of treatment Visit (Week 8, Day 56+/-2, or at early termination), and Visit 7 as follow-up visit (Week 10, Day 70+/-2). The follow-up visit is planned as an on-site visit in case of abnormal laboratory values or unresolved adverse events (AE). Otherwise, the follow-up visit is a telephone interview. At any time during the trial, if judged necessary by the investigator, unscheduled visits may be performed. For a visit schedule, see CTP Section 7.0 [1].

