At all on-site visits (Screening, Week 0, Week 1, Week 4, Week 6, Week 8, and Early Termination), the investigator will assess the extent and severity of the subjects' psoriasis on the body (trunk and/or limbs) using an mPASI scoring system for each of the 3 areas (arms, trunk, and legs). The extent (E) is scored 0 to 6. The severity of the psoriatic lesions in each of the 3 areas will be recorded for each of the signs of redness (R), thickness (T), and scaliness (S). For each clinical sign, a single score, reflecting the average severity of all psoriatic lesions on given body region, will be determined. Redness, thickness and scaliness scores are ranging from 0 to 4. The meaning of scores is summarized in the following table.

Extent (E) Redness (R) Thickness (T) Scaliness (S) Score 0 no involvement none (no erythema) none (no plaque none (no scaling) elevation) <10% mild (slight, barely 1 mild (faint erythema, mild (sparse, finepink to very light red) scale lesions, only perceptible elevation) partially covered) 2 10% to 29% moderate (definite moderate (definite moderate (coarser light red erythema) elevation but not scales, most of thick) lesions covered) 3 30% to 49% severe (dark red severe (definite severe (entire lesion elevation, thick covered with coarse erythema) plaque with sharp scales) edge) 4 50% to 69% very severe (very very severe (very very severe (very dark red erythema) thick plaque with thick coarse scales, possibly fissured) sharp edge) 5 70% to 89% 6 90% to 100%

Table 1: Overview of the meaning of mPASI scores assessed for arms, trunk and legs

Per area, the scores for extent, redness, thickness and scaliness are combined to $A = E \cdot (R+T+S)$. Ranging from a minimum score of 0 and a maximum score of 64.8, the mPASI is calculated from the scores of the extent and severity of the disease by use of the following equation:

 $mPASI = 0.2 \cdot A_{arms} + 0.3 \cdot A_{trunk} + 0.4 \cdot A_{legs}.$

At any post-baseline visit, mPASI 75 is defined as an indicator of a reduction in mPASI from baseline of 75% or more.

PGA and PGA Success on the Body and on the Scalp

PGA measures the investigator's impression of the disease at a single point using a defined, 5-point, static PGA scale (0 = clear, 1 = almost clear, 2 = mild, 3 = moderate or 4 = severe) at Screening, Weeks 0, 1, 4, 6, 8, and Early Termination.

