The PGA assessment will be made separately for the body (trunk and/or limbs) and the scalp. It will represent the *average* lesion severity on the two body locations.

At any post-baseline visit, *PGA success* is defined as a minimum 2-point decrease from baseline to the respective visit on the PGA of psoriasis severity to 0 (clear) or 1 (almost clear).

PTCS

PTCS will be completed by the subjects before any other assessments are performed at Weeks 1, 4, 8, and Early Termination.

The aim of PTCS is to assess the impact and convenience of psoriasis treatment. The scale consists of 6 disease-specific, self-report questions rated on a 10-point scale ranging from 1 to 10. The questions are

- 1. How easy was the treatment to apply to the skin? Answered by 1 = very difficult to 10 = very easy.
- 2. How greasy was the treatment when applying it to the skin? Answered by 1 = very greasy to 10 = not greasy.
- 3. How moisturised did your skin feel after applying the treatment? Answered by 1 = not moisturized to 10 = very moisturized.
- 4. How greasy did your skin feel after applying the treatment? Answered by 1 = very greasy to 10 = not greasy.
- 5. How much did treating your skin disrupt your daily routine? Answered by 1 = very disturbing to 10 = not disturbing.
- 6. Overall, how satisfied were you with the medical treatment? Answered by 1 = not satisfied to 10 = very satisfied.

Ranging from 5 to 50, a PTCS total score is the sum of the scores on questions 1 to 5. If no more than two questions are answered, the PTCS total score is missing. If one or two questions remain unanswered, the missing scores are replaced by the average of the answered scores for the summation.

SGA

Subjects will grade the overall severity of their symptoms according to the following 5-point scale at Weeks 0, 1, 4, 6, 8, and Early Termination:

0 =Clear; no psoriasis symptoms at all.

- 1 = Very mild; very slight psoriasis symptoms that do not interfere with daily life.
- 2 = Mild; slight psoriasis symptoms that interfere with daily life only occasionally.
- 3 = Moderate; definite psoriasis symptoms that interfere with daily life frequently.
- 4 = Severe; intense psoriasis symptoms that interfere or restrict daily life very frequently.

DLQI

The DLQI is a validated questionnaire consisting of 10 questions relating to the degree to which the subject's skin condition affected their daily activities, assessed at Weeks 0, 1, 4, 8, and Early Termination [6]. The questions are

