4.4 Time Points and Time Periods

4.4.1 Periods, Visits and Study Days

The screening period will last from Screening (Visit 0) to randomization (Visit 1/Week 0, Day 0). The treatment period will last from randomization (Visit 1/Week 0) to end of treatment (Visit 6/Week 8 or Early Termination). The follow-up period will last from end of treatment (Visit 6/Week 8) to end of follow-up (Visit 7/Week 10).

Up to six on-site visits are scheduled per subject, at Screening (Visit 0), and Weeks 0, 1, 4, 6 and 8. Visit 1/Week 0 is Day 0, the reference date. In addition, at Week 2, there is a telephone contact planned. Another on-site visit, or a telephone interview, will be held at end of follow-up. Further unscheduled visits may be done as deemed necessary.

Per visit, actual study days will be derived as the time passed in number of days since the reference date plus 1.

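### SAP 4.4.1 and 4.6.2, read literally, let an on-schedule Week 6 visit stand as the observed Week 8 value for a few subjects: study day is defined two ways, and the Week 8 window overlaps the permitted Week 6 days

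*SAP*

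**What the plan says.** **Schedule.** SAP 2.1 places "Visits 2, 4, and 5 at Weeks 1, 4 and 6, respectively, planned for Days 7, 28, and 42 plus/minus 2 days", so Visit 5 (Week 6) may fall on Days 40 to 44. It describes "Visit 6 as end of treatment Visit (Week 8, Day 56+/-2, or at early termination". Protocol Table 7-1 gives the same days.

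**Windows.** SAP 4.6.2 lists the post-baseline targets, "namely at study Day 7, 14, 28, 42, 56 and 70, within two days from target day", and then states: "Comprehensive non-overlapping visit windows are defined for Week 4 from Day 14 to Day 42 and for Week 8 as Day 43 or later". Only follow-up visits are kept out. Within a window, "analysis visits are defined as the visits held closest to the target day per analysis visit window as defined above", with ties going to the later visit. Remaining visits in the window are left out of the primary and secondary endpoint analyses. Weeks 1 and 6 get no window.

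**Study day.** SAP 4.4.1 says "Visit 1/Week 0 is Day 0, the reference date", but a few lines later derives actual study day as elapsed days plus 1. SAP 4.4.2 again makes Visit 1 Day 0.

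**What is scored at Week 6.** For mPASI, "At all on-site visits (Screening, Week 0, Week 1, Week 4, Week 6, Week 8, and Early Termination), the investigator will assess"; PGA is scored at the same visits. By contrast, "PTCS will be completed by the subjects before any other assessments are performed at Weeks 1, 4, 8, and Early Termination".

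**Missing data.** Under SAP 4.7.2 a value is missing only if unavailable, and the imputation has separate steps for Weeks 1, 4, 6 and 8. The tipping-point penalty (5.5.1) applies to imputed Week 8 values, and non-responder imputation (NRI, 5.5.2) applies to missing ones.

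**The concern.** Followed literally, these rules can relabel a visit that the protocol schedules as Week 6 as an observed Week 8 result. The subjects concerned have no usable Week 8 visit. Because the borrowed score counts as available, it is not imputed, does not receive the tipping-point penalty and is not set to non-response, although those rules were written for such subjects. The same visit one day earlier, on Day 42, would leave Week 8 missing and trigger all of them.

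The two definitions of study day make this worse. They move the overlap from the late edge of the Week 6 range to its centre, and two programmers could build different primary datasets from the same text.

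The endpoints reached are percentage change in mPASI, mPASI 75, and PGA success on body and scalp. PTCS has no Week 6 score to carry over.

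**Working it through.** **1. Which day count is intended?** Compare the plan's other figures with each count.

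| Item | Plan | Day 0 count | Plus-1 count |
|---|---|---|---|
| Visit 1 (SAP 4.4.1, 4.4.2) | 0 | 0 | 1 |
| On-target visits (SAP 4.6.2) | 7, 14, 28, 42, 56, 70 | same | 8, 15, 29, 43, 57, 71 |
| Per-protocol Week 8 limit, 49 to 66 days (SAP 4.2.3), against -7/+10 days (protocol 8.3) | -7/+10 | 49 - 56 = -7; 66 - 56 = +10 | 49 - 57 = -8; 66 - 57 = +9 |

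Only Day 0 agrees with the rest of the plan. The plus-1 sentence is the outlier.

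**2. Overlap of the Week 6 range with the Week 8 window (Day 43 or later).**
- Day 0: permitted days 40 to 44; days 43 and 44 overlap; 2/5 = 40%.
- Plus 1: the same visits are study days 41 to 45; days 43, 44 and 45 overlap; 3/5 = 60%. A visit exactly on target is Day 43.

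**3. When does Visit 5 win?** An on-schedule Visit 6 is at most 2 days from Day 56 (3 under plus 1). An overlapping Visit 5 is 11 to 13 days away, so the on-schedule Visit 6 always wins. Under Day 0, Visit 5 is selected only if nothing closer exists:
- Visit 5 on Day 43 is 13 days off. It beats a Visit 6 on Day 70 or later (14 days off) and loses the tie at Day 69.
- Visit 5 on Day 44 is 12 days off. It beats a Visit 6 on Day 69 or later (13 days off) and loses the tie at Day 68.

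**4. Planned precision, as a yardstick.** Protocol 8.2 uses SD 38, 204 per active arm, a 12-point margin and zero difference. SE = 38 x sqrt(2/204) = 3.76. The noncentral t with 406 df gives 88.9% power, matching the stated figure.

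**5. Size under Day 0.** The documents give no rate of subjects without a visit after Week 6. Assumptions: 2 to 10% of an arm, Week 6 visits spread evenly over the five days, Week 6 worse than Week 8 by 2 to 10 points, and imputation recovering that whole gap.
- Subjects per active arm: 204 x 0.02 x 0.4 = 1.6 to 204 x 0.10 x 0.4 = 8.2. Vehicle (68): 0.5 to 2.7.
- Shift in an arm mean: 0.02 x 0.4 x 2 = 0.016 to 0.10 x 0.4 x 10 = 0.40 points. The maximum is 0.40/12 = 3.3% of the margin and 0.40/3.76 = 0.11 SE.
- Visits clustered on target (weights 1-2-3-2-1, so 3/9 overlap): maximum 0.10 x 0.333 x 10 = 0.33.
- Net between active arms: zero if the shifts are equal. If late loss differs by 5 percentage points, 0.05 x 0.4 x 10 = 0.20, or 1.7% of the margin.
- If the plus-1 count were programmed: maximum 0.10 x 0.6 x 10 = 0.60 per arm. With 15% late loss as well: 0.15 x 0.6 x 10 = 0.90, or 7.5% of the margin, before any cancelling.

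**6. NRI analysis of PGA success.** Suppose 11 to 30% of these subjects are successes at Week 6 (the protocol's assumed Week 8 rates for vehicle and active, borrowed as a range). An arm's rate is then higher than under NRI by 0.02 x 0.4 x 0.11 = 0.09 to 0.10 x 0.4 x 0.30 = 1.2 percentage points. The SE of the risk difference at 30% is sqrt(2 x 0.3 x 0.7/204) = 4.54 points, so the maximum is 0.26 SE, again cancelling if equal.

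**7. Windows against imputation.** Under Day 0, a Visit 5 on Days 40 to 42 lies in the Week 4 window and loses to an on-schedule Visit 4. On Days 43 to 44 it lies in the Week 8 window and loses to an on-schedule Visit 6. Read literally, 4.6.2 then drops it from the primary and secondary analyses, yet 4.7.2 needs a Week 6 value as its own step and as a covariate for Week 8.

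**The case against.** The strongest defence is that the windows are prespecified, do not overlap each other, and split at the midpoint of the two analysed targets: (28 + 56)/2 = 42. Using a late on-study score fits a treatment-policy strategy that takes all available data, and nothing shows that imputation would be nearer the truth for these subjects. This stands in part. The boundary itself is defensible; the defect is that no rule keeps a scheduled Week 6 visit out.

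Second, an early-termination assessment on Day 43 would escape imputation, penalty and NRI in the same way. This stands, and the one-day step at Day 42/43 remains for such visits. The difference is that SAP 2.1 makes early termination an occasion for Visit 6, whereas Visit 5 has its own place in the schedule. The SAP should say that this is intended.

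Third, the per-protocol analysis of the primary endpoint uses no imputation and lists a Week 8 limit of 49 to 66 days. Subject to blind review, it should already remove Day 43 and 44 cases. That is a real safeguard, but it does not repair the primary full-analysis-set, tipping-point or NRI analyses.

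Fourth, the late-loss rate is assumed, protocol 5.4 and 7.13 ask sites to secure a Week 8 visit, and the late route needs a Visit 6 roughly when follow-up is due (Day 70 plus or minus 2). All of this stands and limits the size.

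**Conclusion.** Both defects are in the text. The study-day sentence contradicts the rest of the SAP, and even under Day 0 two of the five permitted Week 6 days lie in the Week 8 window. The conflict between the windowing rule and the Week 6 imputation step is also real.

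The numerical effect is small. On the assumptions in step 5 (2 to 10% late loss, a gap of up to 10 points, Day 0), about 2 to 8 subjects per active arm are affected. The arm mean moves by at most about 0.4 points, largely cancelling between the active arms.

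A reader might infer three stronger things that the documents do not support:
- That Week 6 data would widely replace Week 8 data. An on-schedule Visit 6 always wins.
- That the non-inferiority result is at risk. The shift is a small fraction of the margin even at the assumed extremes.
- That on-target Week 6 visits are meant to count as Week 8. That follows only from the plus-1 sentence, which everything else contradicts.

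The affected endpoints appear in 12 of the 13 steps of SAP Table 4 (all but PTCS, step 7), but that describes reach, not size. The tipping-point and NRI analyses are outside the hierarchy. The point merits correction because the rule mislabels a visit and is nearly free to repair.

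**What to change.** Before unblinding:

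1. In SAP 4.4.1, delete the added day so that study day is visit date minus Visit 1 date and Visit 1 is Day 0 throughout. The added day in the duration rule of 4.6.1 is a separate quantity and can stay.
2. In SAP 4.6.2, keep the Day 42/43 boundary but state that a nominal Visit 5 (Week 6) assessment cannot be selected as the Week 8 value. State also that Visit 6, early-termination and unscheduled assessments from Day 43 remain eligible by design under the treatment-policy strategy, and are therefore neither imputed nor penalised.
3. As a required part of the change, state that observed Week 1 and Week 6 values enter the imputation model of 4.7.2 whatever the 4.6.2 windows select. Without this, the Week 6 score of an affected subject could be lost altogether.

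Opening the Week 8 window later, for example on Day 46 or Day 49, would also remove the overlap under either day count. It would, however, discard early-termination assessments made between Day 43 and the new start.

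The cost is SAP wording and one condition in the analysis-dataset derivation; design and sample size are unchanged. The downside is that a few Week 8 values, about 2 to 8 per active arm on the assumptions above, become imputed rather than observed, with the Week 6 score still informing the imputation.

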7.13 Early Termination

The subjects are free to withdraw at any time if they choose without providing reasons. All efforts will be made, however, to encourage the subject to continue in the trial or at least come for the Week 8 visit. This also is applicable in case administration of the IP has been terminated.

If the subject is considered non-compliant with protocol procedures, for example started prohibited medication, all efforts will be made to encourage the subject to continue on treatment (if no safety concerns) or at least come for the Week 8 visit.

The following procedures should be performed at the early termination visit:

- Collect all trial materials from the subject.
- Assess compliance
- Review any concomitant medication used since the previous trial visit.
- Record any AEs.
- Physical examination and vital signs
- Perform a urine pregnancy test for females of childbearing potential.
- Biochemistry and urinalysis.
- PGA
- mPASI
- BSA
- SGA
- DLQI
- EQ-5D
- Psoriasis Treatment Convenience Scale
- Local Skin Reactions

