8.4 Estimands

The efficacy endpoints will be analyzed focusing on two different estimands:

Primary estimand (treatment-policy): the effect of initiating the treatment regimen in subjects with mild-to-moderate psoriasis, with or without any other psoriasis treatment, and whether or not the subject adhered to the treatment regimen.

Thus, for the treatment-policy estimand all available data will be used.

Secondary estimand (hypothetical-strategy): the expected effect in subjects with mild-to-moderate psoriasis if all subjects adhered to the treatment regimen and did not take any other psoriasis treatment (=treatment that according to medical judgement may improve psoriasis).

This is interpreted in the sense that subjects did not initiate other treatment that according to medical judgement may improve psoriasis, and for visits after baseline adhered to the treatment schedule defined as application of IP as specified by the investigator at the previous site visit for at least 70% of the days from baseline visit to Week 4, Week 4 to Week 6 and Week 6 to Week 8. For example, applying IP for 10 out of 14 days is considered adherence, while 9 out of 14 days is not. Thus, for the hypothetical-strategy estimand, only data at or prior to use of other treatment that may improve psoriasis according to medical judgement, and prior to non-adherence to treatment schedule is used. Missing data, data after use of other psoriasis treatment, and data after non-adherence is imputed.

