4.7.2 Missing and Invalid Data

Data is missing if unavailable. Data is invalid if not considered for analysis. Invalidity of data is defined below, where applicable. On some analyses as indicated below, missing or invalid data will be replaced by the last observation carried forward (LOCF), by non-responder imputation (NRI) or by multiple imputation (MI).

Single Imputation by LOCF

On LOCF, a missing value is imputed by the last available value carried forward to the visit with the value missing until and including the last visit.

Single Imputation by NRI

On NRI, a missing value is imputed by a value representing non-response. Non-response is defined per endpoint below.

Multiple Imputation

Post-baseline missing or invalid data will be multiply imputed within treatment groups in two steps [10]. At first, any potential intermediate missing data will be imputed 100 times using a Markov Chain Monte Carlo (MCMC) method to obtain a monotone missing data pattern. In a second step, imputation is done using a monotone regression method, fitting an analysis of covariance (ANCOVA) model stepwise visit by visit. The ANCOVA model adjusts for the effects of analysis sites and baseline PGA as factors and the baseline value of the respective endpoint as a covariate. For each treatment group and each copy of the dataset, the estimated parameters and their variances are used to impute the endpoint. Starting with Week 1, the procedure is repeated on Week 4, Week 6 and Week 8, adding the possibly imputed values of the previous visits as covariates. On MI, missing score data is handled like missing continuous data.

If MI is applied to a dichotomized endpoint, the procedure is followed before dichotomization.

For analyses on the PPS or the safety set, no imputations will be made for missing data. For analyses on the FAS, LOCF, NRI and MI will be made for missing and invalid data.

5 Statistical Methods

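### SAP 4.6.2 drops the early-termination mPASI and PGA of a subject who attends Week 4 on time and leaves later in the Week 4 window, so Week 8 is imputed without the score recorded at withdrawal

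*SAP*

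**What the plan says.** Protocol 7.13 introduces its list with "The following procedures should be performed at the early termination visit"; the list includes PGA, mPASI and the Psoriasis Treatment Convenience Scale (PTCS).

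SAP 4.6.2 sets the windows: "Comprehensive non-overlapping visit windows are defined for Week 4 from Day 14 to Day 42 and for Week 8 as Day 43 or later". Within each window, "analysis visits are defined as the visits held closest to the target day per analysis visit window as defined above". Then: "Any other visits within the same visit window will not be considered for analysis of primary or secondary efficacy endpoints". Ties go to the later visit: "If the time distances of two visits from the target day are identical, the later visit is selected for analysis". The section recognises that ET visits may occur but gives them no slot of their own. Nominal visits are used only for other efficacy endpoints and for safety.

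SAP 4.7.2 describes the multiple imputation (MI): "Starting with Week 1, the procedure is repeated on Week 4, Week 6 and Week 8", with the values at earlier visits as covariates. For last observation carried forward (LOCF), the same section uses the last value available.

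Protocol 8.4 says that "for the treatment-policy estimand all available data will be used". SAP 5.3 repeats this for the primary strategy.

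**The concern.** The primary analysis assumes that data are missing at random given the observed scores. For a subject who leaves because the disease has worsened, the ET score is the observation that makes this assumption credible. Protocol 2.3 expects some subjects to withdraw for inadequate efficacy.

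If the ET score is dropped, Week 8 is imputed from Week 4 and earlier, as though the Week 4 response had held. An arm with more such withdrawals would look better than it is. If that arm is the cream, the non-inferiority comparison leans towards success; if it is the gel, it leans the other way.

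The SAP also gives the Week 6 step of the imputation no window to draw on.

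**Working it through.** **1. Scale, from the plan's own figure.** Protocol 8.2 gives SD 38, 204 per active arm, margin 12, true difference 0 and power 88.9%. The standard error is 38 × √(2/204) = 3.76, and 12/3.76 = 3.19. The normal approximation gives Φ(3.19 − 1.96) = 89.05%; the noncentral t with 406 df gives 88.91%. The stated power is reproduced.

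**2. The rule applied day by day.** Target Day 28, window Days 14 to 42, ties to the later visit, Visit 1 = Day 0.

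| Week 4 visit held on | ET kept (as Week 4) | ET dropped |
|---|---|---|
| Day 26 | Days 27–30 | Days 31–42 |
| Day 27 | Days 28–29 | Days 30–42 |
| Day 28 | none | Days 29–42 |
| Day 29 | none | Days 30–42 |
| Day 30 | none | Days 31–42 |
| missed | Days 14–42 | none |

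Days 31 to 42 are therefore dropped for every Week 4 visit within its ±2-day allowance. An ET visit on Day 43 or later becomes the Week 8 value if nothing nearer Day 56 exists. ET visits on Days 1 to 13 fall in no window.

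A scheduled Week 6 visit (Day 42 ± 2) on Days 40 to 42 lies 12 to 14 days from Day 28 and loses to the Week 4 visit. On Days 43 or 44 it sits in the Week 8 window and loses to a Day 56 visit.

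SAP 4.4.1 counts study days as days elapsed plus one, while 4.4.2 makes Visit 1 Day 0, so each boundary may move by a day.

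**3. Number of subjects (assumption only).** Suppose withdrawals are uniform over 56 days, Week 4 is on Day 28, every leaver has an ET visit and none returns for Week 8. Then 14/56 = 25% of withdrawals fall on Days 29 to 42. With 476 randomised:
- 5% dropout: 476 × 0.05 × 0.25 ≈ 6 subjects
- 10%: ≈ 12
- 20%: ≈ 24

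**4. Size of the bias (assumption only).** Bias in one arm's mean = proportion withdrawing in the window × mean imputation error. Assume percentage changes are normal with SD 35, means −42, −50 and −56 at Weeks 4, 6 and 8, and correlations 0.6 to 0.9.

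- *Strong selection on worsening since Week 4:* the withdrawn subjects' true Week 8 mean is about −41 to −46. Without the ET score it is imputed at about −67, an error of 21 to 26 points.
  - 3%: 0.03 × 21 to 26 = 0.6 to 0.8
  - 5%: 1.1 to 1.3
  - 8%: 1.7 to 2.1
- *Somewhat different settings of the same model* (true −40 to −44, imputed −68 to −70) give up to 2.4 at 8%.
- *Weak selection:* 0.3 to 0.7.
- *Withdrawal driven by the level of disease at ET, at 5%:* 0.3 to 1.2.
- *Withdrawal driven by a mix of change and level, at 5%:* 0.7 to 1.7.
- *Withdrawal unrelated to outcome:* 0.

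With the ET score in the imputation the bias is about zero. This follows from the model, in which withdrawal depends only on scores then observed.

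**5. Consistency.** Under the uniform pattern, 3, 5 and 8% in this window imply total dropout of 12, 20 and 32% (each divided by 0.25). Starting instead from total dropout of 5, 10 and 20% with a 20-point error, the bias is 0.05 × 0.25 × 20 = 0.25, then 0.5 and 1.0.

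**6. Effect on the comparison.** The cream–gel contrast carries the difference between the two arms' biases. Equal biases cancel. Two points in one arm alone would be 2/3.76 = 0.53 of the planning standard error.

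**The case against.** **The plan limits the harm.** Week 8 is imputed only when no visit on Day 43 or later exists, and Protocol 5.4 and 7.13 ask early leavers to attend Week 8. The tipping-point analysis in SAP 5.5.1 penalises imputed Week 8 values, and body PGA success has a non-responder sensitivity analysis. This stands as mitigation, but none of it restores the dropped score.

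**The windows might only label Week 4 and Week 8, with MI using nominal visits.** That would rescue scheduled Week 6 visits. It would not help the ET score: SAP 2.1 places ET under Visit 6 with Week 8, and the imputation chain has no ET step. The wording of 4.6.2 also bars other visits from the analysis outright.

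**Stronger readings that a reader might infer, and that the documents do not support:**
- *That every early ET score is discarded.* If Week 4 was missed, an ET visit on Days 14 to 42 is kept. After a Day 26 or 27 visit, one on Days 29 or 30 can be kept or dropped depending on the days.
- *That the closest-visit sentence removes ET visits before Day 14.* It concerns visits sharing a window, and those days have none. The SAP is silent on them, even though it calls its windows comprehensive.
- *That the PTCS score is certainly lost.* The LOCF text would accept a valid ET score while 4.6.2 would exclude it. This is a conflict to resolve, not a demonstrated loss.
- *That the statement on available data is flatly breached.* In context it can be read as dealing with adherence and other treatment. On that reading the two sections are in tension, but the information is still lost.
- *That non-inferiority is in jeopardy.* The larger biases need strong selection in one arm. Selecting on worsening since Week 4 picks subjects who were above-average responders at Week 4, a debatable picture of efficacy withdrawal.

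**Conclusion.** The point holds in a limited form. Read literally, SAP 4.6.2 drops the ET mPASI and PGA of a subject with an on-time Week 4 visit who leaves later in that window, and Week 8 is then imputed without them if no later visit is held. This is a consequence of a stated rule, not of missing detail. The displaced Week 6 visits, the unassigned Days 1 to 13 and the PTCS conflict have the same source.

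The effect is probably small: roughly 0.3 to 2 points in one arm at 3 to 8% outcome-related withdrawal in the window, against a margin of 12. It is near zero if withdrawal is unrelated to outcome, and it enters non-inferiority only through a cream–gel difference in withdrawal. These sizes rest on assumed means, correlations and selection; the documents give no dropout rate by arm or overall. The change is still worth making because the data are already collected and the rule touches the primary analysis.

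**What to change.** Amend SAP 4.6.2 before unblinding:

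1. Define Week 1 and Week 6 windows for use in the imputation.
2. State that the closest-visit rule does not remove an ET visit held after an attended Week 4 visit and before Day 43. Enter its mPASI and PGA as the observed Week 6 value in the MI chain where no scheduled Week 6 visit was held.
3. Assign ET visits before Day 14 to the nearest unfilled scheduled visit, not automatically to Week 4. If Week 1 is already filled, the next on-site slot is Week 4, which is 15 to 20 days from an ET visit on Days 8 to 13. The SAP should say whether that distance is accepted or the score is left out.
4. Allow a valid ET PTCS score as the LOCF source.
5. Keep Week 8 imputed when no Week 8 visit is held.
6. Settle whether Visit 1 is Day 0 or Day 1.

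The cost is a short SAP clarification and a small programming change, with no new data. The downside is timing: an ET score entered as Week 6 may stand up to about two weeks from its nominal day (Day 29 against Day 42 is 13 days) and may understate response in subjects who were still improving.
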